4.7. Interim Analyses

Limited long-term immunogenicity analyses were performed from ZOSTER-041 Visit 3 (Month 2) to ZOSTER-073 Visit 1 (Day 1) and from ZOSTER-041 Visit 3 (Month 2) to ZOSTER-073 Visit 2 (study Month 12). These intermediate analyses are described in separate project data analysis plans.

A descriptive interim analysis after the revaccination active phase is planned and will be performed one month after the second revaccination dose, study Month 26 (Visit 5). No CSR will be written during the interim analysis. The following will be assessed:

- Long-term safety from ZOSTER-041 Visit 5 (Month 13) to ZOSTER-073 Visit 3 (study Month 24).
- Persistence of immunogenicity from ZOSTER-041 Visit 3 (Month 2) to ZOSTER-073 Visit 3 (study Month 24).
- Safety and immunogenicity after revaccination from ZOSTER-073 Visit 3 (Month 24) to ZOSTER-073 Visit 5 (study Month 26).

The interim analysis will include:

- Primary and secondary immunogenicity endpoints for the LTFU phase and revaccination active phase;
- Secondary safety endpoints for the LTFU phase;
- Reactogenicity data after each administered revaccination dose;
- Unsolicited AEs (serious and non-serious) will also be included up to 30 days follow-up post each revaccination dose;
- SAEs, AESIs (pIMDs and biopsy-proven allograft rejections), withdrawals due to AE and SAEs, confirmed HZ episodes, allograft dysfunctions (following revaccination, HZ episode, and allograft rejection), serum creatinine measurements until the Data Lock Point (DLP).

A final analysis on immunogenicity and safety will be performed at study end (Visit 7) once all data are available and cleaned.

The final study report will contain at least the final analyses of all primary and secondary endpoints. [\[CC1\]](#)

[REDACTED]

[REDACTED]

4.8. Changes to Protocol Defined Analyses

The protocol states the Enrolled Set will be used for analyses of safety and immunogenicity for non-revaccinated subjects, however, the PPS for analysis of persistence (LTFU phase) was amended in this SAP such that it includes Visit 6 (study Month 37) and Visit 7 (study Month 49) for non-revaccinated subjects, therefore, the PPS for analysis of persistence will be used for analyses of immunogenicity and the Enrolled Set will be used for analyses of safety in non-revaccinated subjects.

The protocol states the percentage of subjects reporting at least one SAE related to primary vaccination classified by MedDRA Primary SOC and PT from ZOSTER-041 Day 1 to ZOSTER-073 pre-revaccination will be tabulated with exact 95% CI. Any SAEs related to primary vaccination from ZOSTER-041 Day 1 through the last ZOSTER-041 study visit will be taken from the ZOSTER-041 CSR. Any SAEs that occurred after the last ZOSTER-041 study visit and through ZOSTER-073 pre-revaccination will be captured on the ZOSTER-073 CRFs and summarized according to Section 4.3.2.1.

5. SAMPLE SIZE DETERMINATION

ZOSTER-041 subjects, who had a complete vaccination course (2 doses of HZ/su vaccine) will be offered enrollment into study ZOSTER-073 at participating centers.

Up to a maximum of 86 subjects meeting the eligibility criteria for enrollment (2 doses of HZ/su vaccine in ZOSTER-041) will be targeted for enrollment in participating centers. Approximately 15% of the enrolled subjects might withdraw or not be evaluable for immunogenicity, therefore the target sample size will be approximately 73 subjects evaluable for humoral immunogenicity in the per protocol sets defined in Section 3.

Up to a maximum of 40 subjects will be targeted for the Cell-Mediated Immunity (CMI) sub-cohort in participating centers having CMI capabilities in order to reach 33 evaluable subjects for CMI analyses, assuming a 15% of drop-out and non-evaluability rate. CMI subjects from ZOSTER-041 will be enrolled into the ZOSTER-073 CMI sub-cohort. Also, the balance of CMI subjects to be enrolled will be selected at random from CMI participating centers (having CMI capabilities) to complete the sub-cohort up to 40 subjects at ZOSTER-073 Visit 1 (Day 1).

Subjects who prematurely withdrew from study will not be replaced.

6. SUPPORTING DOCUMENTATION

6.1. Appendix 1 Study Population Analyses

6.1.1. Subject Disposition

The number of subjects enrolled into the study as well as the number of subjects excluded from each analysis set will be presented through a CONSORT table showing the subject disposition

from the Enrolled Set to each PPS as well as the ES. Enrollment by country will be presented as part of demographic summaries.

A summary of the number and percentage of subjects who completed the study as well as those who prematurely withdrew from the study will be provided. Reasons for study withdrawal will be summarized. For those who have neither completed nor withdrawn, they will be categorized as in follow-up. This analysis will be based on the Enrolled Set.

A summary of study intervention status will be provided. This display will show the number and percentage of subjects who have completed each dose of the scheduled study vaccine, are ongoing with study intervention, or have discontinued study intervention prematurely, as well as primary reasons for discontinuation of study intervention. This analysis will be based on the ES.

6.1.2. Demographic and Baseline Characteristics

The demographic characteristics including age (in years at the time of primary vaccination in ZOSTER-041, in years at the time of enrollment in ZOSTER-073, and in years at first revaccination in ZOSTER-073), gender, ethnicity, baseline weight and race will be summarized with descriptive statistics. In addition, the following age categories will be summarized: 18-49, and ≥ 50 YOA (according to subgroups), as well as 18-64, 65-84 and ≥ 85 YOA (needed for publishing) based on the Enrolled Set. Age will be calculated as the number of years between the date of birth and the date of primary vaccination/enrollment/re-vaccination. Missing demographic variables will not be replaced.

Demographic summaries will be provided overall, by age at the time of primary vaccination in ZOSTER-041, and by maintenance immunosuppressive therapy at the time of primary vaccination in ZOSTER-041.

Medical history since the last study ZOSTER-041 visit will be listed. Uncoded medical history will be summarized under 'Other' category. Medical history for subjects with confirmed, probable, and suspected diagnosis of COVID-19 AEs can be obtained from the medical history listing.

Renal transplant rejection history and replacement kidney will also be listed for the Enrolled Set. Smoking history will be part of the medical history listing.

6.1.3. Protocol Deviations

Important protocol deviations including those related to COVID-19 will be summarized and listed. Protocol deviations which result in exclusion from an analysis set will also be summarized. Data will be reviewed prior to freezing and locking the database to ensure all deviations leading to analysis population exclusions are captured and categorised in the protocol deviations ADaM dataset.

There are also situations that are not deviations, but would require an elimination, e.g. a participant may elect or not be eligible to be revaccinated, and are excluded from revaccinated

set but included in long-term follow-up from primary vaccination series. These will be summarized with the protocol deviations resulting in exclusion.

6.1.4. Prior and Concomitant Medications and Vaccinations

The number and percentage of subjects with concomitant medications (including the following immunosuppressive therapy categories: maintenance, therapeutic, and chronic use and well as anti-viral treatment for HZ, pain rescue medication to control HZ pain, and other therapy for HZ as well as pain rescue medication to control HZ pain and other therapy for HZ) will be summarized during the 30-day follow-up period after each vaccine administration and overall. While maintenance and therapeutic immunosuppressive therapies are used for prevention of transplant rejection, a chronic use immunosuppressive therapy is for a different purpose yet may have still an impact on immune response so will also be tabulated.

Concomitant vaccinations and concomitant immunosuppressive medications will be listed. Concomitant medications and vaccinations will be coded using both the GSK Drug and WHO Drug dictionaries. Anatomical Therapeutic Chemical (ATC) classifications will appear in the listing. Duration of therapeutic immunosuppressive therapy will be displayed in the listing of concomitant medications.

Concomitant COVID-19 vaccination before and during the study will be presented with concomitant vaccination/vaccination history listings.

6.1.5. Study Intervention Compliance

The number of doses administered will be tabulated as will the percentage of subjects who have completed each dose of the scheduled study vaccine.

The number and percentage of subjects who returned the dairy cards and those who returned the dairy cards with documentation of the presence or absence of AEs will be tabulated for the ES. Compliance in completing solicited AEs information will be tabulated after each dose and overall.

Summaries of the time intervals between study visits will be tabulated based on the Enrolled Set.

6.1.6. Additional Analyses Due to the COVID-19 Pandemic

Depending on how the COVID-19 pandemic evolves, the SAP may be amended to reflect the additional analyses corresponding to COVID-19.

6.2. Appendix 2 Data Derivations Rule

This section contains standard rules for data display and derivation for clinical and studies.

6.2.1. Baseline Immunogenicity

For the LTFU phase, baseline is latest non-missing pre-primary series dose assessment from ZOSTER-041 study. For non-revaccinated subjects, at ZOSTER-073 Visit 6 and Visit 7, baseline is also latest non-missing pre-primary series dose assessment from ZOSTER-041 study.

For the revaccination active and follow-up phases, baseline is the latest pre-revaccination dose assessment with a non-missing result from ZOSTER-073.

6.2.2. Assessment Window

For data summaries by visit, scheduled visits with nominal visit description will be displayed. Unscheduled visits will not be displayed or allocated into a visit window. All unscheduled visits will be displayed in the listing.

6.2.3. Multiple measurements at One Analysis Time Point

Baseline and post-baseline serum creatinine measures are computed as follows:

- For Allograft rejection:
 - The average of measurements 2 months prior to a biopsy-proven allograft rejection will be used as event baseline. If there are not 2 or more measurements in 2 months, then go back to 3 or 4 months prior to biopsy to have a minimum of 2 measurements.
 - The maximum of measurements taken up to 2 months after resolution of the biopsy-proven rejection, so that 2 or more additional post-rejection measurements are recorded, will be used to determine declining allograft function compared to baseline pre-allograft rejection measurements.
- For revaccination:
 - The average of measurements taken 3 months prior to first revaccination, Visit 3 (Month 24), will be used as pre-vaccination baseline. If there are not 3 or more measurements in 3 months, then go back to 4 or 5 months prior to revaccination to have a minimum of 3 measurements.
 - The maximum of measurements taken up to 3 months after last revaccination, Visit 5 (Month 26), so that 3 or more additional post-revaccination measurements are recorded, will be used to determine declining allograft function compared to pre-revaccination
- For episode of HZ cases:
 - The average of measurements taken 2 months prior to a HZ episode, will be used as event baseline. If there are not 2 or more measurements in 2 months, then go back to 3 or 4 months prior to HZ episode to have a minimum of 2 measurements.
 - The maximum of measurements taken up to 2 months after HZ episode rash resolution, so that 2 or more post-HZ resolution measurements are recorded, will be used to determine declining allograft function compared to pre-HZ episode.
- For non-revaccinated subjects:

- The mean of the available values before primary vaccination is used as baseline value.
- The maximum of the available values after Visit 3 Month 24 up to study end is used for calculating fold increase

As described in Section 1.2, since the interval between the end of ZOSTER-041 study and the start of this ZOSTER-073 study will vary per subject, yearly timeframes will be defined around the anniversary date post vaccination for the first ZOSTER-073 blood sample and incremented by 1 year each visit after. As such, the same interval may include one subject's data from ZOSTER-073 Visit 1 and another subject's Visit 2 data due to overlapping in timepoints by study year associated with the long-term follow-up phase.

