8.1.8. Pre-revaccination body temperature

The oral (preferred route) body temperature of each subject needs to be measured prior to any study vaccine administration and recorded in the eCRF. If the subject has fever [fever is defined as temperature $\geq 38.0^{\circ}\text{C}$ (100.4°F) regardless of route of measurement] on the day of vaccination, the revaccination visit will be rescheduled within the allowed interval for this visit (see [Table 4](#)). ***Pre-revaccination temperature measurements should not be performed for non-revaccinated subjects.*** **(Amended: 15 June 2020)**

CONFIDENTIAL212340 (ZOSTER-073 EXT:041 Y4-10)
Protocol Amendment 1 Final**8.1.9. Record serum creatinine measures**

As the detection of kidney allograft function is paramount to the management of allograft health and prevention of allograft rejection, transplant centers have established vigorous routine clinical surveillance protocols for the monitoring of the allograft. This study will rely on these per site “surveillance protocols” and will not mandate the type or timing of tests to participating study sites.

To follow allograft function, the available serum creatinine measurements, obtained per the site’s “surveillance protocol” or for “clinical indication” (locally available), will be recorded in the eCRF.

Record ALL serum creatinine obtained:

- **For Allograft rejection**

- For 2 months prior to a biopsy-proven allograft rejection, as event baseline. If not 2 or more measurements in 2 months, then go back to 3 or 4 months prior to biopsy to have a minimum of 2 measurements.
- From onset of allograft rejection through resolution.
- For 2 months after resolution of the biopsy-proven rejection and the cessation of therapeutic immunosuppressive therapy, so that 2 or more additional post-rejection measurements are recorded.

Post-allograft rejection serum creatinine measurements will be evaluated in comparison to the subject’s baseline pre-allograft rejection measurements.

- **For revaccination**

- For 3 months prior to first revaccination, Visit 3 (Month 24), as pre-vaccination baseline. If not 3 or more measurements in 3 months, then go back to 4 or 5 months prior to revaccination to have a minimum of 3 measurements.
- From Visit 3 (Month 24) through Visit 5 (Month 26).
- For 3 months after last revaccination, Visit 5 (Month 26), so that 3 or more additional post-revaccination measurements are recorded.

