	
 Allograft function for episode(s) of allograft rejection. 
 Occurrence of allograft dysfunction through assessment of all clinically obtained serum creatinine measures from 2 months prior to an episode of biopsy-proven rejection and up to 2 months after rejection resolution and cessation of therapeutic immunosuppressive therapy for the time period from study ZOSTER-041 last visit (Month 13) to study ZOSTER-073 Visit 3 (Month 24). Allograft function for episode(s) of HZ 
 Occurrence of allograft dysfunction through assessment of all clinically obtained serum creatinine measures from 2 months prior to an episode of HZ and up to 2 months after HZ rash resolution for the time period from study ZOSTER-041 last visit (Month 13) to study ZOSTER-073 Visit 3 (Month 24).
Revaccination active phase - Immunogenicity assessment 
 To evaluate cell-mediated immunity post- revaccination Doses 1 & 2. 	
In revaccinated subjects in CMI sub-cohort:
 
 Frequencies of gE-specific CD4+ T-cells expressing two or more markers such as IFN-γ, IL-2, TNF-α, CD40L as determined by ICS at pre-vaccination (Month 24) and at 1-month post-revaccination Dose 1 (Month 25) and Dose 2 (Month 26).
Revaccination follow-up phase – Immunogenicity assessment 
 To evaluate persistence of humoral and cell-mediated immune responses post-revaccination Dose 2. 	
In all revaccinated subjects:
 
 Anti-gE antibody concentrations as determined by ELISA at 12 months and 24 months post-revaccination Dose 2. 
In revaccinated subjects in CMI sub-cohort:
 
 Frequencies of gE-specific CD4+ T- cells expressing two or more markers such as IFN-γ, IL-2, TNF-α, CD40L as determined by ICS at 12 months and 24 months post-revaccination Dose 2 in a CMI sub-cohort of subjects.

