	
 – Occurrence, intensity of unsolicited AEs during 30 days after each revaccination (i.e., the day of revaccination and 29 subsequent days) and causal relationship to revaccination by investigator assessment. • SAEs 
 – Occurrence of SAEs (including fatal SAEs) from Dose 1 of revaccination (Month 24) until 12 months post-last revaccination dose (Month 37). – Occurrence of related-SAEs (including related-fatal SAEs) as per investigator assessment from Dose 1 of revaccination (Month 24) up to study end (Month 49). • AESIs 
 – Occurrence of all biopsy-proven allograft rejections from Dose 1 of revaccination (Month 24) up to study end (Month 49) and causal relationship to revaccination by investigator assessment. – Occurrence of pIMDs from Dose 1 of revaccination (Month 24) up to 12 months post-last revaccination dose (Month 37) and causal relationship by investigator assessment. • HZ episodes 
 – Occurrence of confirmed HZ cases from Dose 1 of revaccination (Month 24) up to study end (Month 49). • Allograft function following revaccination 
 – Occurrence of allograft dysfunction through assessment of all clinically obtained serum creatinine measures from 3 months before the first revaccination dose until 3 months after the last revaccination dose. • Allograft function for episode(s) of allograft rejection 
 – Occurrence of allograft dysfunction through assessment of all clinically obtained serum creatinine measures from 2 months prior to an episode of biopsy-proven rejection and up to 2 months after rejection resolution and cessation of therapeutic or immunosuppressive therapy. • Allograft function for episode(s) of HZ 
 – Occurrence of allograft dysfunction through assessment of all clinically obtained serum creatinine measures from 2 months prior to an episode of HZ and up to 2 months after HZ resolution.

Objectives	Endpoints
CCI	Tertiary

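### SAP 6.2.3 ends the post-rejection creatinine window without the therapy-cessation anchor that the endpoint carries, and gives the window no start

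*SAP*

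**What the plan says.** SAP 6.2.3 sets the two values that enter the fold change for a rejection episode. The baseline is a mean: "The average of measurements 2 months prior to a biopsy-proven allograft rejection will be used as event baseline", with a look-back to 3 or 4 months if fewer than 2 values exist. The post-event value is "The maximum of measurements taken up to 2 months after resolution of the biopsy-proven rejection", and the sentence goes on "so that 2 or more additional post-rejection measurements are recorded, will be used to determine declining allograft function". For herpes zoster (HZ) the post-event value is "The maximum of measurements taken up to 2 months after HZ episode rash resolution".

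SAP 4.5.3.1 refers to 6.2.3 for these definitions, so 6.2.3 governs the tabulated fold-increase tiers (1.2, 1.5, 1.75 and 2). SAP 4.3.2.1 and 4.3.2.2 define dysfunction as a 1.2-fold or greater increase.

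The endpoint is worded differently. For the long-term follow-up phase, SAP 1.1 runs the creatinine assessment "up to 2 months after rejection resolution and cessation of therapeutic immunosuppressive therapy for the time period" from the last ZOSTER-041 visit to Visit 3. For the revaccination phase it runs to "2 months after rejection resolution and cessation of therapeutic or immunosuppressive therapy". Protocol Table 5 carries the cessation anchor in both phases, with small wording differences. Protocol 8.1.9 collects creatinine in three separate periods: before the rejection, from onset through resolution, and "For 2 months after resolution of the biopsy-proven rejection and the cessation of therapeutic immunosuppressive therapy". It then compares post-rejection values with the pre-rejection baseline.

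**The concern.** There are two gaps between the derivation rule and what it is meant to derive.

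First, the end of the window. The rule counts 2 months from resolution alone, whereas the endpoint counts from resolution and cessation of therapeutic immunosuppression. A creatinine rise after rejection therapy is withdrawn could fall inside the endpoint window and outside the derivation.

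Second, the start of the window. A maximum taken up to a date, with no date to count from, leaves open whether onset-to-resolution values belong. Because the statistic is a maximum, one such value can settle the classification. Two programmers working from this text could report different counts from the same data on a graft-safety endpoint.

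**Working it through.** The documents give no figure to reproduce here. The check is a comparison of texts, followed by an illustration on assumed values.

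**Texts side by side (rejection episodes)**

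| Source | Post-event window starts | Window ends |
|---|---|---|
| Protocol 8.1.9 | after resolution and cessation; onset-to-resolution is a separate period | 2 months after resolution and cessation |
| Protocol Table 5 and SAP 1.1 (endpoint) | not separated: all values from 2 months before the episode | 2 months after resolution and cessation |
| SAP 6.2.3 (derivation) | not stated | 2 months after resolution |
| SAP 4.8 (declared changes) | not mentioned | not mentioned |

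The HZ end date in SAP 6.2.3 agrees with Protocol 8.1.9 and the long-term follow-up endpoint. Only its start is missing.

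Two features of SAP 6.2.3 make the open start matter. The rule for non-revaccinated subjects does state a start (after Visit 3), so its absence elsewhere is noticeable. The revaccination rule uses the same form of words, and there the endpoint does cover values from the first dose onward. Programming all the rules alike would therefore bring in-episode values into the rejection maximum.

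**End of window.** Let L be the months from resolution to cessation of therapeutic immunosuppression, with L > 0. The SAP window ends at 2 months and the endpoint window at 2 + L. For L = 1, 3 and 6 the endpoint window ends at 3, 5 and 8 months, so 1, 3 and 6 months are lost. If therapy stops at or before resolution, nothing is lost.

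**Effect on classification.** Fold = maximum in the window / baseline mean, counted if 1.2 or more. All creatinine values are assumed: baseline 1.4; peak = maximum from onset to resolution; post = maximum in the 2 months after resolution; late = maximum in the added period up to 2 months after cessation.

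- A: no start, SAP end = max(peak, post) / 1.4
- B: start at resolution, SAP end = post / 1.4
- C: start at resolution, end 2 months after the later of resolution and cessation = max(post, late) / 1.4

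| Peak | Post | Late | A | B | C |
|---|---|---|---|---|---|
| 1.7 | 1.45 | 1.5 | 1.21 yes | 1.04 no | 1.07 no |
| 1.7 | 1.45 | 1.9 | 1.21 yes | 1.04 no | 1.36 yes |
| 2.8 | 1.6 | 1.9 | 2.00 yes | 1.14 no | 1.36 yes |
| 2.1 | 1.8 | 1.5 | 1.50 yes | 1.29 yes | 1.29 yes |
| 1.65 | 1.45 | 1.9 | 1.18 no | 1.04 no | 1.36 yes |

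Including in-episode values can only raise the maximum. Ending the window early can only lower it or leave it unchanged. The last row shows that the missing anchor can change the result under either reading of the start.

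**Weight of one subject.** SAP Table 1 gives 68 enrolled. One reclassified subject is 1/68 = 1.5 percentage points if all enrolled subjects form the denominator, and more if only subjects with an episode do. The SAP does not say which, and neither document states an expected number of episodes.

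**The case against.** A reader might infer that the maximum will be the acute rejection peak, so that almost every rejection counts as dysfunction automatically. The documents do not support that. They nowhere say that rejections are usually found through a creatinine rise, and Protocol 8.1.14 also dates rejections from surveillance biopsies, which need not coincide with one. A peak of 1.65 on a baseline of 1.4 is 1.18-fold and would not count. The reference in SAP 6.2.3 to post-rejection measurements, and the description in SAP 4.3.2.1 and 4.3.2.2 of decline following the episode, suggest that a post-resolution window was intended. Taking in the peak is a permitted reading, not a certainty.

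A reader might also infer that including in-episode values contradicts the endpoint window. It does not: that window takes all measures from 2 months before the episode and so already spans it. The conflict over the start is with the post-rejection comparison in Protocol 8.1.9. Nor do the documents say that the endpoint's purpose is to show recovery; it is the occurrence of dysfunction.

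Much of the detail will be visible in any case. SAP 4.5.3.1 lists every creatinine value with its fold increase, SAP 4.3.2.2 lists rejection dates, treatment and outcome, and SAP 6.1.4 lists the duration of therapeutic immunosuppression. That limits the harm, but the tabulated count would still depend on an unstated choice. The missing anchor and the missing start both stand.

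**Conclusion.** The point holds as a discrepancy in the derivation rule. Followed as written, SAP 6.2.3 leaves out creatinine values that the endpoint requires whenever therapeutic immunosuppression stops after resolution, and SAP 4.8 does not declare this. The absent start, for rejection and for HZ, leaves the in-episode values undecided.

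The size in this trial cannot be computed, because the documents give neither episode counts nor the lag between resolution and cessation. The fold changes shown rest on assumed values and establish only that the classification can move in either direction. The endpoint is secondary and descriptive, no hypothesis test or error rate depends on it, and the effect is confined to subjects with a rejection or HZ episode.

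**What to change.** In SAP 6.2.3:

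- **Rejection:** start the post-rejection window at resolution and end it 2 months after the later of resolution and cessation of therapeutic immunosuppression. Starting at the later of the two dates would be worse, because it would discard values between them.
- **HZ:** run the window from rash resolution to 2 months after.
- **In-episode values:** tabulate the onset-to-resolution maximum in a separate row. Count unresolved rejections there, using all available values. Protocol 8.1.14 allows a rejection to be ongoing or to progress to graft failure, and such an episode would never open a post-resolution window.
- **If the shorter window is intended:** list the removal of the cessation anchor in SAP 4.8 and give the reason.

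The cost is a change of wording and one extra table row. No new data are needed: Protocol 8.1.9 already collects the creatinine values over the longer window, and Protocol 7.5.1 already records therapeutic immunosuppression for biopsy-proven rejections from Visit 1.
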